volumetrics: Our prior 6-12 month PA interventions in children, young adults, and older adults have used between 20^26 and 60^40 subjects per group with moderate-sized effects (Cohen's d) ranging between 0.30 and 0.50. Crosssectional research has supported these numbers with studies reporting significant effects of PA on brain volume with only 32 subjects and slightly larger effect sizes between 0.50 - 0.60. Even if we estimate a rather conservative effect size of 0.30, 60 participants per group is sufficient to detect differences in brain volume at 80% power. Diffusion imaging: Changes in white matter have been detected in PA interventions in as little as 6-months with only 50 subjects. In a 12-month exercise intervention, we found increased FA with only 35 subjects in each group with an estimated effect size of 0.70^28. Fewer results have been reported in midlife, but in children, effects of PA on white matter have been reported with N=25/group. Based on an estimated effect size of 0.75, we should have 90% power with 60 participants per group to test our main hypotheses as well as enough power for exploratory analyses. Connectivity: With only 65 people, we have shown that a 12-month exercise intervention is effective at enhancing functional connectivity in prefrontal-inhibitory networks. The difference between the groups for PFC connectivity was .15 with a standard deviation of .10 suggesting an effect size of 1.5 (Cohen's d). In young adults, we report similar effects with N=50 with increased functional connectivity between the anterior hippocampus and ACC. Therefore, similar to the effect sizes and power for the other neuroimaging measures, 60 participants per group should be sufficient for detecting changes as a function of the intervention with 95% power. Stress reactivity and affect: In preliminary data from the AHAB2 cohort, greater PA was associated with reduced daily life stress reactivity measured by strain (r=.23) and conflict (r=.25). In a 12-week exercise intervention in young adults with major depression scores on the Montgomery Asberg Depression Rating Scale significantly decreased from 21.8 to 4.25, and the magnitude of this decrease was correlated with increases in fitness (r=-.39). Based on these effect size data, 60 participants per group would provide us with >90% power to detect an effect on stress and affect measures. Thus, we estimate adequate power to test Aim 2. CVD markers: Prior randomized exercise interventions examining some of the same CVD risk markers proposed here (e.g., baroreflex sensitivity [BRS]) are typically between 4-52 weeks in duration with  $N=\sim10$  and  $150^{31}$ . Despite this heterogeneity, meta-analyses of exercise interventions show moderate-to-large effects on many of these outcomes (Cohen's d=.60). For example, a meta-analysis of 30 exercise interventions on multiple CVD risk markers reported an average 18 week duration with  $\sim 50$  subjects in each study ( $\sim 25/\text{group}$ ). In this metaanalysis, CRF increased by 3.04 mL/kg/min with a Cohen's d of 0.58. We expect larger effect sizes here because durations of ~1-year demonstrate larger changes in these metrics. Thus, based on prior studies and meta-analyses, we are sufficiently powered with N=150 to test for exercise-induced changes in CVD markers. Mediation: Using established empirical estimates of sample sizes needed for .80 power in bias-corrected bootstrapping analyses with moderate sized effects in both alpha and beta, it is estimated that 115 participants are needed. Thus, based on the above effect sizes for both brain and CVD markers, we are

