**1.4.3 MEDIATION:** Aim 1 has two hypotheses, (a) to test whether the peripheral effects of exercise mediate brain effects, and (b) whether the effects of exercise on the brain mediate the beneficial effects of exercise on peripheral mediators of CVD risk. We propose to test these hypotheses using longitudinal mediation models in a structural equation modeling (SEM) framework. Aim 1A: In this model, the exercise groups (X) are proposed to influence visceral control circuits (Y) via changes in peripheral pathways (M) including insulin resistance, oxidative stress, endothelial dysfunction, and CRF. We will first examine whether brain or these peripheral CVD pathways can be summarized as latent variables to control for measurement error. When using latent variables, the modeling will proceed by first establishing well-fitting measurement models, and testing for measurement invariance across waves. To test the hypothesis proposed in Aim 1A, analyses will be conducted both on a voxel-wise basis (e.g., using the BRAVO Toolbox (https://sites.google.com/site/bravotoolbox/)) or using extracted data from SPM, FSL, or FreeSurfer, depending on the imaging modality and analysis. In the latter case, we will use a theory-driven approach by selecting values from anatomical or functionally-defined regions-of-interest (ROI) on visceral control regions. Each imaging modality will be analyzed in separate models unless we have a theoretical or empirical basis for including multiple imaging metrics in a single model. We will use standard cluster-based and FDR corrections for multiple comparisons for all voxel-wise analyses and the Brain Connectivity Toolbox for graph theory metrics (i.e., segregation). Although directional hypotheses have been posited for our mediation analyses, a more conservative significance will be set at .01 to limit inflation of type 1 error. Global and incremental model fit will be verified using multiple fit-indices (chi-square, RMSEA, CFI, TLI, SRMR). With three waves of data, we will use full longitudinal mediation to test our hypotheses. Full longitudinal mediation allows us to test the effect of initial standing on the hypothesized predictor (X – Exercise group) at T1 on change in the mediator (M – peripheral CVD markers) from T1 to T2, controlling for initial standing on M, and the effect of the mediator (M– peripheral CVD measures) at T2 on the change in the outcome (Y – change in brain measure) from T2 to T3, controlling for initial value of the outcome. Mediation will be tested by calculating the indirect effect of paths that are consistent with longitudinal mediation (i.e., paths a and b in Fig. 1). Here the estimate a\*b provides a measure of the longitudinal mediated effect because it represents the effect of X at T1 on residualized change in M (path a), and M at T2

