
on residualized change in Y (path b). Significance of the mediation (i.e., indirect) effect will be examined using techniques that account for non-normality in the parameter distribution, namely bias corrected bootstrapping-based approaches. A benefit of full longitudinal mediation models is that the direction of the paths can be reversed (Y->M->X) to test for the opposite causal direction, and bidirectional effects can similarly be tested. We will test for these possibilities by comparing models with paths reversed and allowing bi-directional effects. Finally, we aim to explore the role of other potential mediators (i.e., sleep) and moderators (e.g., gender) on the direction and strength of associations. Aim 1B: We will proceed with similar approaches described above for Aim 1A including using a voxel-wise approach and a theory-driven approach by selecting anatomical or functionallydefined ROIs on visceral control circuits or the white matter pathways that connect them. Importantly, there may be regional dissociations between the brain regions identified in Aim 1A and those identified in Aim 1B. Using voxel-wise analyses, we will be able to adjudicate the regional specificity or overlap between the regions identified in Aim 1A with those of Aim 1B. Using these procedures, we will also be able to determine the specificity of particular effects (e.g., regions associated with BRS but not with HRV) or differences across imaging metrics (e.g., differences of effect between functional connectivity, cortical thickness, white matter). With three waves of data, we will use full longitudinal mediation to test our hypotheses that X (Exercise group) influences BRS, HRV, and glucocorticoid control (Y) via its effects on brain plasticity on visceral control circuits (M). The description of the SEM modeling approach for Aim 1A will be applied to test mediation for Aim 1B. To test Aim 2A & B: The analytical plans for testing Aim 2A and 2B along the lines depicted in the heuristic model of Figure 1 will proceed like that described above for Aim 1A and B. That is, we will test how the effect of the hypothesized predictor (X – Exercise group) influences the change in the mediator (M – visceral control circuits), on stress reactivity and affect metrics that are measured in Projects 1-2 (e.g., EMA and ABP measures identical to those used in NOAH). Similar to Aim 1, we will be able to model opposite causal directions and bidirectional effects by reversing the paths in the model and will be able to determine specificity of particular effects (e.g., regions associated with emotion regulation, but not daily life stress reactivity) or differences across imaging metrics (e.g., differences of effect between functional connectivity, cortical thickness, white matter). As above, we will also test other potential mediators (i.e., sleep) and moderators (e.g., gender) on the direction and strength of associations.

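### If the mediation SEM uses latent variables, their invariance is tested across waves but not across randomised arms, so an exercise effect on one indicator can bias path a

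*Combined protocol and SAP*

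**What the plan says.** Section 1.4.3 MEDIATION describes Aim 1A as exercise group acting on the brain "via changes in peripheral pathways (M) including insulin resistance, oxidative stress, endothelial dysfunction, and CRF". It will first "examine whether brain or these peripheral CVD pathways can be summarized as latent variables to control for measurement error". If latent variables are used, "the modeling will proceed by first establishing well-fitting measurement models, and testing for measurement invariance across waves". This is the only invariance test named.

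Of the indirect effect a*b, the section says "it represents the effect of X at T1 on residualized change in M (path a", so path a is an arm contrast on M between baseline and month 6. The threshold is given as "a more conservative significance will be set at .01 to limit inflation of type 1 error". A further check is listed: "Global and incremental model fit will be verified using multiple fit-indices (chi-square, RMSEA, CFI, TLI, SRMR". It has no cut-offs and no stated action on failure.

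For Aim 1B, "The description of the SEM modeling approach for Aim 1A will be applied to test mediation for Aim 1B", and Aim 2 is to be analysed along the same lines. The Amendments in Study Protocol section reduces the target to 120 and makes the SEM mediation exploratory.

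**The concern.** A latent M turns several markers into one number. The arm effect on that number means what its label says only if arm shifts each indicator in proportion to its loading. If exercise also acts directly on one indicator, the model has nowhere to put that shift except the factor, and path a absorbs part of it.

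Invariance across waves does not address this. It asks whether intercepts and loadings are the same at months 0, 6 and 12. The disturbance here lies between arms at the follow-up waves. Randomisation makes the arms comparable at baseline, not at month 6.

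CRF is the obvious candidate, because aerobic training acts on it directly. Section 1.4.1 POWER cites a meta-analysis in which "CRF increased by 3.04 mL/kg/min with a Cohen's d of 0.58". If CRF rose and the other markers did not, a latent M could show an arm effect under a label that also covers insulin resistance, oxidative stress and endothelial function. Aim 1A is meant to distinguish among such mechanisms.

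**Working it through.** **Inputs from the documents.** 120 randomised, equal allocation, 20% attrition: 120 × 0.8 = 96, or 48 per arm. CRF effect d = 0.58. Threshold .01, taken as two-sided. Four indicators of M are named.

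**The plan's own power figures first.** With 48 per arm, the two-sample noncentrality is d × √(48/2) = 4.899d. Two-sided alpha .05 gives:
- d = 0.50: 68.8%
- d = 0.58: 81.1%
- d = 0.60: 83.6%

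These agree with the amendment's 68-83% for hippocampal volume and >80% for CVD biomarkers. The point disputes neither figure.

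**Assumptions not in the documents.** One factor with four standardised indicators at two waves, factor stability 0.7, unique parts correlated 0.5 across waves. The true path a is 0, and exercise raises CRF alone by 0.58 SD at month 6. Five loading sets (CRF / other three) are used.

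**Hand check.** With loadings λ held fixed and unique variances θ = 1 − λ², the factor shift that best fits a CRF-only change is approximately

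a ≈ (λ_CRF × 0.58 / θ_CRF) ÷ Σ(λ²/θ).

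- For .6/.6 this reduces to 0.58 ÷ (4 × 0.6) = 0.24.
- For .8/.4 it is (0.8 × 0.58 / 0.36) ÷ (0.64/0.36 + 3 × 0.16/0.84) = 1.289 ÷ 2.349 = 0.55.

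**Full fit.** Maximum-likelihood SEM with mean structure was fitted to the population moments, with loadings equal across waves. Rejection rates come from the noncentral chi-square with noncentrality 96 × ΔF, where ΔF is the difference in fit function. The wave test has 3 df and the global chi-square 27 df, both at .05. Repeat fits move some entries by about one point.

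| Loadings CRF/others | False path a (SD) | Significant at .01 | Wave test flags | Global chi-square rejects | Path a, intercepts freed |
|---|---|---|---|---|---|
| .6/.6 | 0.23 | 8% | 67% | 71% | 0.23 |
| .7/.5 | 0.53 | 42% | 49% | 55% | 0.46 |
| .8/.4 | 0.57 | 78-79% | 22% | 25% | 0.57 |
| .5/.6 | 0.18 | 5% | 65% | 68% | 0.18 |
| .4/.6 | 0.13 | 3% | 63% | 66% | 0.14 |

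For .8/.4, path a has noncentrality 96 × 0.1156 = 11.1 on 1 df. The wave test in the model containing arm has 96 × 0.0250 = 2.40 on 3 df, which gives 22%. Run with the arms pooled, it has 96 × 0.0437 = 4.20, which gives about 38%. The low end of wave-test detection is therefore 22% or 38%, depending on how the test is set up.

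**Sensitivity outside the five sets.**
- Equal loadings of 0.4: false path a 0.61 SD, significant at .01 in 56%, wave test 53% (arms pooled), global chi-square 34%.
- Equal loadings of 0.8: 0.14 SD, 4%, 88% (arms pooled) and 95%.

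**After the fix.** A direct path from arm to CRF returns path a to 0.00 in every set. Its 1-df test at .05 has 79-99% power with intercepts equal across waves and 63-93% with them free.

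**The case against.** Much can be said for the plan.

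- **Latent variables are conditional.** With single observed markers the problem does not arise. This stands. But the plan examines the latent route first, and the invariance sentence governs exactly that route.
- **The SEM is exploratory** since the amendment, and the primary endpoints are analysed by mixed model on observed measures. This stands. A reader might infer that the trial's main results are at risk; the documents do not support that.
- **Global fit is to be verified.** It catches the problem in about 25-71% across the five sets, and in 18-44% once intercepts are freed across waves. This is a real but partial safeguard, without cut-offs or an action on failure.
- **The largest figure comes from an extreme set.** In .8/.4 the other three markers correlate only 0.4 × 0.4 = 0.16 with one another. Composite reliability is (0.8 + 3 × 0.4)² ÷ [(0.8 + 3 × 0.4)² + 0.36 + 3 × 0.84] = 4 ÷ 6.88 = 0.58. Such a factor is close to CRF alone and may not survive the plan's first step.
- **The CRF-only scenario is constructed.** Section 1.4.1 POWER cites effects of about 0.60 on many CVD markers, so the sponsor expects several to move together. CRF-only is possible, not predicted.
- **Some markers are analysed singly.** Section 1.4.3 PRIMARY OUTCOMES lists CRF, pulse wave velocity and vasodilation among the further outcomes, so a CRF-only pattern would be partly visible. It does not name insulin resistance or oxidative stress, and nothing requires these results to be read beside the latent one.

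Two stronger readings are tempting. One is that a false path a produces a false mediation finding. It does not by itself: inference is on a*b by bias-corrected bootstrap, a false a*b also needs a non-zero path b, and no rate for a*b was computed. The other is that a brain latent would be biased to a similar degree if exercise acts mainly on the hippocampus. Nothing here quantifies that, and the planned region-of-interest and voxel-wise analyses already address regional specificity.

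**Conclusion.** The gap is real but narrow. If a latent variable is used, the named invariance test does not cover the comparison that path a makes, and it can be passed while path a is biased. Under the stated assumptions the false effect is 0.13 to 0.57 latent SD over the five loading sets. It is significant at .01 in 3-79%, with three of the five sets at 8% or less. The obvious repair after a failed wave test, freeing intercepts across waves, leaves 0.14 to 0.57 SD.

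All of this depends on assumed loadings, stability and residual correlation, and on a CRF-only effect. The rates describe path a alone. What is exposed is the labelling of an exploratory mechanism, not the primary endpoints. The change is still worth making, because the remedy removes the bias in this set-up and costs little.

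**What to change.** In section 1.4.3 MEDIATION, require measurement invariance across waves and across randomised arms, and carry this over to Aims 1B and 2. Specifically:

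1. Before a latent variable is used in path a or b, test a direct path from arm to each indicator at months 6 and 12, or equivalently test equal intercepts between arms.
2. Where a direct effect is found, keep that path in the model, or take the indicator out (CRF, for example) and model it as its own observed variable.
3. Report the arm effect on each indicator, including insulin resistance and oxidative stress, beside the latent result.
4. Apply the same check to any brain latent as a precaution.

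The cost is about a sentence in the plan and a few extra model fits, with no change to data collection. Where a direct path is kept, the model gains one or two parameters and the latent effect is estimated slightly less precisely.

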#### **1.3 PRELIMINARY DATA:**

- 1. Peripheral mediators and markers of CVD risk and PA: In the AHAB2 registry, we tested associations between markers and mediators of CVD risk and PA after control for age and sex. In AHAB2, energy expenditure (assessed over ~5 days by actigraphy) was negatively correlated with mean carotid intima-media thickness (p = 0.017, N = 437) and an aggregate metabolic risk score (p < 0.001, N = 414). Also, energy expenditure was positively correlated with an index of cardiac vagal control derived from high-frequency heart rate variability (HF-HRV) and root mean square of successive differences (RMSSD) measured during paced and unpaced breathing epochs (p < 0.001, N = 432). Moreover, greater energy expenditure correlated with lower interleukin 6 (IL-6) and C-reactive protein (CRP) (ps < 0.001, Ns = 453 and 454). The cardiac vagal control index also negatively correlated with IL-6 and CRP (p's < 0.005, Ns = 448 and 449). In line with our aims, energy expenditure was positively correlated with bilateral hippocampal volume after additional control for intra-cranial volume (ICV) (p = 0.024, N = 425). Finally, the cardiac vagal control index was positively correlated with volumes of the ACC, amygdala, and hippocampus (ps < 0.05). Implications for this project: These results show associations between PA and peripheral markers and mediators of CVD risk, and that these associations may be linked to markers of brain plasticity and health. What is unknown, and what is tested here, is whether such cross-sectional associations between CVD risk markers, PA, and brain health are causally linked in the context of an experimental manipulation of PA.
- 2. **PA**, **stress**, **and affect**: In brief, we replicate several observations from the literature on associations between PA and fitness with affect, and we provide the first

evidence that PA relates to blunted stressor-evoked BP reactivity in daily life. We also report the first associations to our knowledge on PA and individual differences in neural activity during the processing of negative emotional stimuli, as well as during the regulation of negative emotions. In aggregate, these initial findings support the integration of the fMRI stressor and emotion task batteries, as well as ambulatory (ABP) and ecological monetary assessment (EMA) methods.

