
sufficiently powered to test our hypotheses using structural equation modeling even after attrition. In sum, our planned sample size of 150 (N=75 per group) will be sufficient for allowing us to test our primary hypotheses.

**1.4.2. PRELIMINARY STEPS**: Prior to hypothesis testing, all data will be examined to determine: 1) frequency distributions for missing data and out-of-range values; 2) normality and internal consistency of subscales; and, 3) association between variables that may be highly correlated to guard against multicolinearity, which would inflate standard errors and make estimation

[figure not shown]

Figure 1. Diagram of exemplar full longitudinal mediational model. Paths involved in estimating longitudinal stability and residualized change are in black, paths involved in mediation are in red, and non-essential parameters are grayed out for legibility.

unstable. We will also examine the distribution of factors between groups to assess whether covariate-adjustment is required. Missing data: All outcomes will be tested using an intent-totreat (ITT) framework. Sensitivity will be explored using adherence to the intervention (e.g., per protocol). We will report reasons for dropouts and explore missing data mechanisms. To examine whether missingness is unrelated to other observed and unobserved measurements (missing completely at random, MCAR) or to the observed measurements only (missing at random, MAR), testing for completely random dropouts will be carried out. Additional sensitivity analyses test for informative dropouts. We will apply pattern-

mixture models by stratifying our data by dropout patterns and fitting separate regression models to strata.

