#### 1.6 **RANDOMIZATION**:

After the completion of the baseline measures and sessions described above the participants will be randomly assigned to one of two groups. These include (a) an exercise condition that will consist of 150 minutes per week of moderate-to-vigorous intensity exercise, or (b) a PA and health information group. We will use a computer randomization protocol that will incorporate a verification that all session visits have been completed and data entered into the database. We will use a minimization algorithm with equal allocation to one of the two groups. The use of the minimization strategy will ensure treatment balance on the two factors of age at study entry (=<42, >42) and gender. Once randomized, an assigned staff member will contact the participant via phone with the group information. On this contact, the staff member will give information such as date, day, time, and location of the subject's first intervention session.

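### In the exploratory mediation models the mediator-to-outcome path is not randomised, and beyond earlier M and Y the only stated covariate rule (imbalance between arms) cannot pick out its confounders

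*Combined protocol and SAP*

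**What the plan says.** Section 1.4.3 Mediation defines the analysis for Aim 1A and carries it over to Aims 1B, 2A and 2B. "Mediation will be tested by calculating the indirect effect of paths that are consistent with longitudinal mediation", namely a (arm to change in M from baseline to 6 months, "controlling for initial standing on M") and b (M at 6 months to change in Y from 6 to 12 months, "controlling for initial value of the outcome"). The product a*b is tested by a bias-corrected bootstrap at .01. The section adds that "the direction of the paths can be reversed (Y->M->X) to test for the opposite causal direction".

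Only arm is randomised. Section 1.6 describes minimisation for "treatment balance on the two factors of age at study entry (=<42, >42) and gender".

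On covariates, section 1.4.2 says: "We will also examine the distribution of factors between groups to assess whether covariate-adjustment is required". Section 1.4.3 Primary Outcomes also allows for confounders, but names none, and the sentence concerns the mixed model for the primary outcomes. In the mediation text, sleep appears only as another possible mediator and gender only as a moderator. There is no statement that unmeasured M-Y confounding is assumed absent, and no sensitivity analysis for it.

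On purpose, section 1.3 says that the trial tests whether associations between "CVD risk markers, PA, and brain health are causally linked in the context of an experimental manipulation of PA". The aims in section 1.0 are milder and speak of statistical mediation and partial explanation. The section headed Amendments in Study Protocol reduces the target from 150 to 120 and makes the mediation work exploratory, because of power.

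**The concern.** Path b is an observational regression inside a trial. Anything that moves both a peripheral marker and a brain measure, in either arm, makes M at 6 months predict later change in Y even if M has no effect on Y. Multiplied by a real effect of exercise on M, this looks like exercise working through M.

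A check of balance between arms is the wrong tool for finding such a factor. A common cause that is independent of arm is balanced in expectation, so the check flags it only at the chance rate. Age and gender are plausible common causes, yet the minimisation is designed to keep them balanced, so an imbalance rule is especially unlikely to select them.

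At stake is the reading of a significant a*b. It could be reported as evidence of a pathway, and a comparison of forward and reversed models as evidence of causal direction, when a shared cause would produce the same result.

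**Working it through.** The plan gives no figure for this bias. Its one figure for the mediation test, 115 participants for .80 power, is a cited value without the sizes of a and b, and nothing below depends on it.

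**Inputs from the documents.** Analysed N = 120 × 0.8 = 96, or 48 per arm (amendment). As a check that 48 per arm is the amended basis: a two-sided t-test at .05 with noncentrality d√(48/2) gives 67.9% power at d = .5 and 82.9% at d = .6, matching the stated 68-83%. Effect of exercise on M: d = .58 to .60 (section 1.4.1, CVD markers). Threshold .01, taken as two-sided.

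**Assumptions.** True b = 0. One common cause U, independent of arm, induces an M-Y correlation r of 0, .1, .2 or .3. The documents give no value for r.

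**Simple calculation.** P(a significant): noncentrality .60 × √24 = 2.94, giving about .62 at .01. P(b significant), by Fisher's z with √(96 − 3) = 9.64 and critical value 2.576:
- r = .1: atanh(.1) × 9.64 = 0.97, probability .054
- r = .2: 1.96, probability .27
- r = .3: 2.98, probability .66

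Multiplied by .62, these give about 3%, 17% and 41%. With r = 0 the product is .62 × .01 = 0.6%.

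**Three-wave simulation.** M and Y each had stability .6 between waves, and d = .58. M at 6 months was regressed on arm and baseline M. Y at 12 months was regressed on arm, baseline M, baseline Y, 6-month Y and 6-month M. In one setting U affects only the changes. In the other U is stable and also affects baseline M and Y, and r is then the correlation that U induces before earlier values are adjusted for. The test was either joint significance (both paths at .01) or the planned bias-corrected bootstrap (600 trials, 1,000 resamples).

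| False-positive rate for a*b, N = 96 | r = 0 | .1 | .2 | .3 |
|---|---|---|---|---|
| Simple product | 0.6% | 3% | 17% | 41% |
| U on changes only, joint significance | 1% | 4% | 19% | 51% |
| U on changes only, bootstrap | 1.8% | 7% | 26% | 61% |
| Stable U, joint significance | 1% | 2% | 7% | 12% |
| Stable U, bootstrap | not run | not run | not run | 20% |

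The simulated rates for U on changes exceed the simple product partly because adjusting for baseline M makes path a easier to detect.

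**What the plan's safeguards do.**
- *Balance check.* A t-test between arms at .05 flagged U in 3.5% to 6% of trials. Where U was not flagged, the false-positive rate was essentially unchanged (62% against 61% overall, r = .3, U on changes).
- *Earlier M and Y.* These help when U is stable. At r = .3 the mean estimate of b was .16, against about .30 when U acts only on the changes. They do not remove the bias.
- *Sample size.* More participants do not help. With the bootstrap, r = .3 and U on changes, the rate is 77% at N = 120 against 61% at N = 96.
- *Reversed paths.* With a common cause acting between waves (strength .3, no true effect either way, N = 96), the forward path b was significant at .01 in 36% of trials and the reverse path in 37%, against about 1% each with no common cause.
- *Adjusting for U in both equations.* The bootstrap rate was 0.8% to 2.5% at N = 96.

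**The case against.** The strongest reply is that the amendment has already made these analyses exploratory. That stands and lowers the stakes. The stated reason is power, however, so the downgrade neither acknowledges nor removes the bias. Section 1.4.3 Primary Outcomes still gives the structural equation models the role of testing the project's aims.

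A reader might infer that imbalance between arms is the plan's only protection. It is not: the models condition on earlier M and earlier Y, which takes out part of any stable confounding. Most obvious candidates (age, adiposity, habitual fitness) are of the stable kind, where the rates are much lower.

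A reader might also infer that the mediation models are offered as proof of causation. The documents do not go that far. The aims speak of statistical mediation, and the causal phrase in section 1.3 contrasts cross-sectional data with a randomised manipulation of activity. The clearer causal claim is the use of reversed paths to test direction. Effects in both directions would at least warn against a one-way conclusion, so reversal is not useless, but it cannot separate mutual influence from a shared cause.

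Finally, the upper end of the range is demanding. With a single common cause equally related to both, r = .3 needs a correlation of √.3 = .55 with each residual change, that is 30% of each variance. The hippocampal result in section 1.3 (p = .024, N = 425) corresponds to r of about 2.26/√425 = .11. That is a different, cross-sectional quantity, but nothing in the documents supports .3.

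Figure 1 is not shown in the text available here, so covariates or residual covariances drawn in it cannot be ruled out. The written plan mentions none.

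**Conclusion.** The point holds as a cheap improvement of low to moderate severity. Path b is not protected by randomisation. Beyond earlier M and Y, the only stated covariate rule cannot select the factors that would confound it. The .01 threshold limits chance findings, not this bias.

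With no true b and N = 96, the false-positive rate for a*b is about 1-2% without a common cause. For an assumed r of .1 to .3 it is roughly 2-12% for a stable common cause (about 20% at r = .3 with the planned bootstrap), and roughly 3-61%, depending on the test, for one acting only on the changes. The strength of confounding and the stability of .6 are assumptions, so these figures show sensitivity and do not predict what will happen in this trial. In particular, the documents do not support reading 41% or 61% as the expected error rate. The randomised comparisons of the primary outcomes are not affected.

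**What to change.** 1. In both the M and the Y equations, for all mediation aims, include a pre-specified set of baseline covariates chosen as predictors of M and Y and not by imbalance between arms. Candidates already collected are age, gender, BMI from height and weight, baseline VO2max where it is not itself M, baseline actigraphy measures of activity and sleep, and diet. Use baseline values only, because exercise may change weight, sleep and fitness after randomisation.
2. State that path b rests on the assumption of no unmeasured M-Y confounding. For each significant a*b, report the residual M-Y correlation at which its interval would include zero.
3. Baseline covariates cannot remove time-varying or unmeasured confounding. Report results as *consistent with mediation*, not as proof of a causal link, and describe the reversed-path models as a comparison of model forms, not as a test of causal direction.

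Cost: SAP wording, a few degrees of freedom per equation and one extra sensitivity analysis. No new data are needed.
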